7.1.8 Interim Analysis

Efficacy

Updating of the posterior distribution for ORR will commence after the first 12 patients have either

completed 4 cycles of therapy or withdrawn from the study, or earlier if requested by the TMC or sponsor. Publication of the posterior distribution for ORR will occur after all patients remaining on the study, at the time of the decision to close accrual, have completed 4 cycles of therapy or have subsequently withdrawn.

Safety Lead-in Evaluation

A safety lead-in evaluation will be performed by the Trial Management Committee (TMC) after the first 6 patients to commence ITD combination therapy have completed 1 cycle of ITD combination therapy or withdrawn earlier. The safety lead-in will be based on listings of adverse events and no formal statistical analysis is planned.

Continuous Monitoring and Early Stopping Rule

Safety will continue to be monitored after every additional cohort of 6 patients completes 1 cycle of ITD combination therapy or withdraws earlier, or, at anytime as requested by the TMC or sponsor. In particular, the rate of grade 3 or higher non-haematological toxicities will be monitored and the posterior probability that this rate exceeds 33.3% will be reported, based on a minimally informative prior distribution for the rate, namely, Beta($a=0.5$, $b=1$) for which the median rate is 25%. The TMC or sponsor will consider early stopping or modification of the trial if the observed rate exceeds 35% and the posterior probability that the true rate exceeds 33.3% is more than 50%. For $n=12$ (or 36) patients, the probability that both these criteria are met is 0.05 when the true rate is 18.0% (or 22.9%) and 0.80 when the true rate is 49.9% (or 41.7%).

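### The trigger probabilities quoted at n=36 for the safety stopping rule are for one isolated look; over the scheduled looks the chance of meeting the criteria by n=36 is 0.18 at a 22.9% true rate, not 0.05

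*Protocol*

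**What the plan says.** All of this is in Protocol section 7.1.8.

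- **Frequency.** Under the heading on continuous monitoring and early stopping: "Safety will continue to be monitored after every additional cohort of 6 patients completes 1 cycle of ITD combination therapy or withdraws earlier". Looks may also take place "at anytime as requested by the TMC or sponsor".
- **First 6 patients.** "The safety lead-in will be based on listings of adverse events and no formal statistical analysis is planned". The first formal application of the rule is therefore at n=12.
- **Criteria.** Stopping or modification is considered "if the observed rate exceeds 35% and the posterior probability that the true rate exceeds 33.3% is more than 50"%. The prior for the rate of grade 3 or higher non-haematological toxicity is Beta(0.5, 1), "for which the median rate is 25"%.
- **Force.** "The TMC or sponsor will consider early stopping or modification of the trial". The rule is advisory.
- **Stated performance.** "For $n=12$ (or 36) patients, the probability that both these criteria are met is 0.05 when the true rate is 18.0% (or 22.9"%), and 0.80 at 49.9% (n=12) or 41.7% (n=36). No probability accumulated over the repeated looks is given.

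**The concern.** The paragraph schedules looks at 12, 18, 24, 30, 36 and 42 patients, and the criteria can be met at any of them. A probability for n=36 that takes no account of the four earlier looks does not describe the rule as it will be run.

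Safety is a co-primary objective, and this is the protocol's only quantitative safety stopping rule. A committee that reads 0.05 at 22.9% as the chance that the rule ever fires by 36 patients would misjudge what a trigger tells it. It would underrate how often a trigger arises at that rate. It would also underrate how readily the rule picks up a high rate.

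**Working it through.** **Inputs (section 7.1.8; planned enrolment of 45 from section 4.2).** Prior Beta(0.5, 1); criteria observed rate > 35% and Pr(true rate > 33.3%) > 50%; formal looks at n = 12, 18, 24, 30, 36, 42.

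**Step 1: trigger counts.** With x events in n patients the posterior is Beta(0.5 + x, 1 + n − x). The trigger count is the smallest x that meets both criteria. The table compares x = n/3, which fails both, with the next count up.

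| n | x = n/3: rate, posterior probability | x = n/3 + 1: rate, posterior probability | Trigger |
|---|---|---|---|
| 12 | 33.3%, 0.475 | 41.7%, 0.701 | 5 |
| 18 | 33.3%, 0.480 | 38.9%, 0.669 | 7 |
| 24 | 33.3%, 0.483 | 37.5%, 0.648 | 9 |
| 30 | 33.3%, 0.485 | 36.7%, 0.634 | 11 |
| 36 | 33.3%, 0.486 | 36.1%, 0.623 | 13 |
| 42 | 33.3%, 0.488 | 35.7%, 0.615 | 15 |

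**Step 2: reproduce the stated figures as single looks**, using Pr(X ≥ c) for X ~ Binomial(n, p).

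- n=12, c=5: 0.049 at p=0.180 and 0.804 at p=0.499.
- n=36, c=13: 0.051 at p=0.229 and 0.801 at p=0.417.

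All four agree with the stated 0.05 and 0.80, so the protocol's figures are single-look probabilities.

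**Step 3: accumulate over the scheduled looks.** Let f_n(s) be the probability of s events at look n with no trigger so far. For the next cohort of 6,

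f_{n+6}(s) = Σ_k f_n(s − k) · C(6,k) · p^k · (1 − p)^(6−k).

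The mass at or above the trigger count is added to the cumulative probability and removed before the next step. The first step uses the Binomial(12, p) distribution. The calculation is exact.

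| True rate | by 12 | by 18 | by 24 | by 30 | by 36 | by 42 | Stated for n=36 |
|---|---|---|---|---|---|---|---|
| 18.0% | 0.049 | 0.060 | 0.064 | 0.067 | 0.068 | 0.068 | – |
| 22.9% | 0.117 | 0.149 | 0.165 | 0.175 | 0.182 | 0.186 | 0.05 |
| one third | 0.369 | 0.468 | 0.531 | 0.575 | 0.609 | 0.635 | – |
| 41.7% | 0.609 | 0.735 | 0.807 | 0.853 | 0.886 | 0.909 | 0.80 |
| 49.9% | 0.804 | 0.904 | 0.949 | 0.971 | 0.983 | 0.990 | – |

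At 22.9% the looks contribute 0.1174 + 0.0312 + 0.0166 + 0.0100 + 0.0064 = 0.1816 by n=36. That is about 3.6 times the single-look value (0.182/0.051).

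**Step 4: invert.** The true rates at which the cumulative probability is 0.05 and 0.80 are 16.8% and 38.4% by n=36, and 16.8% and 37.5% by n=42.

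**Sensitivity to the schedule.** With only two looks, at 12 and 36, the figure at 22.9% is already 0.142. The result does not depend on counting every intermediate look.

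**The case against.** The strongest reply is that nothing in the sentence is miscalculated. It gives probabilities for a named n, all four reproduce, and it does not call them cumulative. An attentive reader could also see that if 18.0% gives 0.05 at n=12, then 22.9% must give more than 0.05 there. That is right as far as it goes: a reader might infer an arithmetic error, and there is none. But the n=36 pair is the only performance given for the rule at that stage, and it stands in a paragraph that schedules four earlier looks. The sentence neither labels the figures as per-look nor shows how far repetition moves them. A statistical analysis plan might hold a fuller table, but the figures at issue are fixed in the protocol.

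Four stronger readings are tempting and are not supported:

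- **That the n=12 figures are wrong too.** They are not. The review of the first 6 patients uses listings without formal analysis, so n=12 is the first formal look, and at that point the single-look and cumulative probabilities coincide. At 18.0% the cumulative figure rises only to 0.068 by n=36.
- **That the trial has an 18% chance of being stopped at 22.9%.** The text only has the committee or sponsor consider stopping or modification, so 0.18 is the chance of prompting that discussion.
- **That 22.9% is a rate the protocol regards as tolerable.** The protocol gives it no such status; it is the rate at which the single-look probability equals 0.05.
- **That frequent triggering near one third is a defect.** That is the rule's own toxicity threshold, and review there is what it is for.

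Repeated looks also raise detection at 41.7% from 0.80 to 0.89, so the omission understates the rule's sensitivity as well. This limits the harm but leaves the description incomplete.

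**Conclusion.** The point holds as a mismatch between the stated operating characteristics and the monitoring schedule. By n=36, over the scheduled looks, the probability that both criteria have been met at least once is 0.18 at 22.9% (stated 0.05) and 0.89 at 41.7% (stated 0.80); at one third it is 0.61. The thresholds themselves are not in question.

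Assumptions: formal looks exactly at 12, 18, 24, 30 and 36 (and 42 where stated), none at 6, and independent patients sharing one fixed probability of the monitored event, which is the model behind the protocol's own figures. Unscheduled looks can only raise the cumulative values. Whether toxicities after cycle 1 count is not stated. A reader might want to settle that by limiting the rule to cycle 1, but that would narrow a safety rule; it is a separate design choice and no part of this point.

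**What to change.** In section 7.1.8, label the present figures as probabilities at a single look and add the cumulative ones over the scheduled looks:

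- Trigger counts: 5/12, 7/18, 9/24, 11/30, 13/36, 15/42.
- Probability that the criteria are met at least once by n=36: 0.05 at 16.8%, 0.18 at 22.9%, 0.61 at one third, 0.80 at 38.4%, 0.89 at 41.7%.
- The same by n=42: 0.05 at 16.8%, 0.19 at 22.9%, 0.64 at one third, 0.80 at 37.5%.
- A note that looks made on request can only increase these probabilities, and that meeting the criteria leads to consideration of stopping or modification, not to automatic stopping.

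The cost is one sentence and a small table. Thresholds, prior, look schedule and sample size are unchanged. The one drawback is that the stated chance of a trigger at the lower rates becomes less favourable.

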8. ADVERSE EVENTS

8.1 Definitions

8.1.1 Adverse Event Definition

Adverse event (AE) means any untoward medical occurrence in a patient or subject administered a pharmaceutical product; the untoward medical occurrence does not necessarily have a causal relationship with this treatment. An AE can therefore be any unfavorable and unintended sign (including an abnormal laboratory finding), symptom, or disease temporally associated with the use of a medicinal (investigational) product whether or not it is related to the medicinal product. This includes any newly occurring event, or a previous condition that has increased in severity or frequency since the administration of study drug.

An abnormal laboratory value will not be assessed as an AE unless that value leads to discontinuation or delay in treatment, dose modification, therapeutic intervention, or is considered by the investigator to be a clinically significant change from baseline.

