3. STUDY ENDPOINTS

3.1 Primary Endpoints

The primary efficacy endpoint is the achievement of an overall response (sCR + CR + VGPR + PR + MR) as defined by International Myeloma Working Group (IMWG) criteria while on ITD combination therapy.

The co-primary safety endpoints are the incidence and severity of adverse events while on ITD therapy and the tolerability endpoints are total dose and percentage of planned dose of each study drug delivered in each cycle.

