7.1.7 Safety Analysis

The co-primary objective of the trial is to evaluate the safety and tolerability of ITD combination therapy. These evaluations will be conducted on the Safety Set. Treatment emergent adverse events, i.e. newly occurring or worsening AE's that occur after the first dose of study drug, will be defined as per the CTCAE v4.03 and will be summarised by system organ class and/or preferred term as counts and percentages of participants with further subdivision based on severity and relationship to ITD therapy. Particular attention will be given to (i) rates of peripheral neuropathy (either sensory and/or painful) and cardiac toxicities \geq Grade 2, (ii) cessation of ixazomib and/or thalidomide and/or dexamethasone due to unacceptable toxicity, and (iii) subject withdrawal due to unacceptable toxicity. Total dose and percentage of planned dose (PPD) will be summarized, by cycle, for each of ixazomib, thalidomide and dexamethasone and will also be summarized for the accumulated first 4 cycles of ITD therapy. PPD is the total dose delivered divided by the per-protocol planned total dose, expressed as a percentage. The summaries of total dose and PPD will consist of means, standard deviations, medians, 25th and 75th percentiles, minima and maxima. Listings of worst grades of toxicities, by patient and cycle and up to 30 days after the last dose of study drug, will be generated as an Appendix to the report

of the primary analysis and, as required, for the TMC or sponsor.

Adverse events will be tabulated according to the NCI CTCAE version 4(19), as a guideline, whenever possible will include the following categories:

Treatment-emergent AEs

- ☐ Drug-related treatment-emergent AEs
- ☐ Grade 3 or higher treatment-emergent AEs
- ☐ Grade 3 or higher drug-related treatment-emergent AEs
- ☐ The most commonly reported treatment-emergent AEs (ie, those events reported by 10% of all patients)
- ☐ Serious adverse events

A listing of treatment-emergent AEs resulting in study drug discontinuation will be provided.

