serious, which is based on patient/event outcome or action criteria described above, and is usually associated with events that pose a threat to a patient's life or ability to function. A severe AE (Grade 3 or 4) does not necessarily need to be considered serious. For example, a white blood cell count of 1000/mm³ to less than 2000 is considered Grade 3 (severe) but may not be considered serious. Seriousness (not intensity) serves as a guide for defining regulatory reporting obligations.

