8.2 Procedures for Reporting Serious Adverse Events

AEs may be spontaneously reported by the patient and/or in response to an open question from study personnel or revealed by observation, physical examination, or other diagnostic procedures. Any clinically relevant deterioration in laboratory assessments or other clinical finding is considered an AE. When possible, signs and symptoms indicating a common underlying pathology should be noted as one comprehensive event. For serious AEs, the investigator must determine both the intensity of the event and the relationship of the event to study drug administration.

AEs which are serious must be reported to Millennium Pharmacovigilance (or designee) from the first dose of study drug through 30 days after administration of the last dose of ixazomib. Any SAE that occurs at any time after completion of ixazomib treatment or after the designated follow-up period that the sponsor-investigator and/or sub-investigator considers to be related to any study drug must be reported to Millennium Pharmacovigilance (or designee). In addition, new primary malignancies that occur during the follow-up periods must be reported, regardless of causality to study regimen, for a minimum of three years after the last dose of the investigational product, starting from the first dose of study drug. All new cases of primary malignancy must be reported to Millennium Pharmacovigilance (or designee).

Planned hospital admissions or surgical procedures for an illness or disease that existed before the patient was enrolled in the trial are not to be considered AEs unless the condition deteriorated in an unexpected manner during the trial (e.g., surgery was performed earlier or later than planned). All SAEs should be monitored until they are resolved or are clearly determined to be due to a patient's stable or chronic condition or intercurrent illness(es).

Since this is an investigator-initiated study, the principal investigator [name], also referred to as the sponsor-investigator, is responsible for reporting serious adverse events (SAEs) to any regulatory agency and to the sponsor- investigator's EC or IRB.

Regardless of expectedness or causality, all SAEs must also be reported in English to Millennium Pharmacovigilance (or designee):

Fatal and Life Threatening SAEs within 24 hours of the sponsor-investigator's observation or awareness of the event

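### Section 8.1.1 counts a laboratory value as an adverse event only if it is acted on or judged significant, so the AE-only co-primary safety tables may under-count graded, mainly haematological, toxicity

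*Protocol*

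**What the plan says.** Section 3.1 makes adverse events a co-primary endpoint: "The co-primary safety endpoints are the incidence and severity of adverse events while on ITD therapy". Section 7.1.7 says that treatment-emergent events "will be defined as per the CTCAE v4.03 and will be summarised by system organ class and/or preferred term as counts and percentages of participants". Every table it then lists (all, drug-related, Grade 3 or higher, most common, serious) is a table of AEs.

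The protocol describes when a laboratory value becomes an AE in four places:

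- Section 8.1.1, first paragraph, is broad: "An AE can therefore be any unfavorable and unintended sign (including an abnormal laboratory finding), symptom, or disease".
- Section 8.1.1, second paragraph, narrows this: "An abnormal laboratory value will not be assessed as an AE unless that value leads to discontinuation or delay in treatment, dose modification". The sentence continues with two further routes: "therapeutic intervention, or is considered by the investigator to be a clinically significant change from baseline".
- Section 8.1.2 uses a white cell count of 1000/mm3 "to less than 2000 is considered Grade 3 (severe) but may not be considered serious" to show that a severe AE need not be a serious one. The value is graded on its size alone.
- Section 8.2 uses different words again: "Any clinically relevant deterioration in laboratory assessments or other clinical finding is considered an AE".

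The Schedule of Events collects FBE and biochemistry at screening, on Day 1 of each cycle, on Day 15 of cycles 1 to 3 and at end of treatment. Section 7.1.7 also plans appendix listings of worst toxicity grade by patient and cycle, and allows further safety summaries if appropriate.

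**The concern.** A CTCAE laboratory grade depends on the measured value. The filter in section 8.1.1 depends on what somebody did or thought about that value. When a table counts only events that pass the filter, the reported incidence and severity of laboratory toxicity partly reflect the dosing rules, local supportive-care practice and investigator habit. Leaving values out can only lower the counts, so any bias is downward.

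This matters because incidence and severity of AEs is a co-primary endpoint, there is no comparator arm that would share the same under-counting, and ixazomib is expected to affect blood counts. Section 6.7 gives thrombocytopenia and neutropenia their own management paragraphs.

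**Working it through.** The plan gives no figure for this point, so the check follows laboratory values through the rules as written.

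**Thresholds.** A new cycle needs ANC of at least 1,000/mm3 (1.0 x10^9/L) and platelets of at least 75,000/mm3 (75 x10^9/L); otherwise dosing is delayed (section 6.3.1). Within a cycle, drug is withheld at platelets of 30 or less or ANC of 0.50 or less on a dosing day other than Day 1, or at ANC of 1.0 or less with fever at any time (Table 6-2). Neither place has a threshold for total white cells, lymphocytes or haemoglobin.

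**Values traced through the rules** (blood counts in x10^9/L unless stated):

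| Result | Day 1 of a later cycle | Day 15, cycles 1 to 3 |
|---|---|---|
| Platelets 60 | Below 75: delay, so an AE | Above 30: no hold; AE only if treated or judged significant |
| ANC 0.9, no fever | Below 1.0: delay, so an AE | Above 0.50: no hold; AE only if treated or judged significant |
| White cells 1000 to <2000/mm3 (Grade 3 per 8.1.2) | No white-cell criterion; AE only if treated or judged significant | Same |
| Related Grade 3 biochemistry | Hold under Table 6-3, so an AE | Hold under Table 6-3, so an AE |

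The first two rows show the same value counted differently by calendar day. For those rows, the range that no dosing rule reaches on Day 15 is platelets >30 to <75 and afebrile ANC >0.5 to <1.0, provided the count has recovered by the next Day 1. A count that has not recovered causes a delay and enters then. The third row shows that the protocol's own example of a severe AE can fail its own test for being an AE.

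**The remaining routes.** Section 6.5 leaves growth factors to published guidelines or institutional practice and transfusions to institutional guidelines. Section 6.7 makes growth-factor support for neutropenia optional. The same ANC can therefore be an AE at a site that treats it, and depend on opinion at a site that does not. This shows how counts could differ between sites; it is not evidence that they will.

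**Biochemistry.** Section 6.3.1 exempts isolated GGT rises only from the criteria for starting a cycle. The Grade 3 row of Table 6-3 has no such exemption, so a related Grade 3 GGT rise is held and becomes an AE. Other related non-haematological toxicity above Grade 1 delays the next cycle and is also counted. The gap is therefore mainly haematological.

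**Stopping rule in section 7.1.8.** The rule needs an observed rate above 35% and a posterior probability above 50% that the true rate exceeds 33.3%, with a Beta(0.5, 1) prior. With x events in n patients the posterior is Beta(0.5 + x, 1 + n - x).

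- n = 12: the smallest x meeting both criteria is 5 (posterior probability 0.700; 0.474 at x = 4). P(X >= 5) is 0.049 at a true rate of 18.0% and 0.804 at 49.9%; the protocol states 0.05 and 0.80.
- n = 36: the smallest x is 13 (0.622; 0.485 at x = 12). P(X >= 13) is 0.051 at 22.9% and 0.801 at 41.7%; the protocol states 0.05 and 0.80.

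The stated figures reproduce. The rule counts only Grade 3 or higher non-haematological toxicity, so the blood-count range above does not enter it.

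**The case against.** The strongest reply is that the filter is a deliberate definition. On that view, CTCAE in section 7.1.7 supplies terms and grades for events already accepted as AEs and need not turn every gradable value into one. The clinical-relevance wording of section 8.2 is also close to the significance route in section 8.1.1, so the conflict between those two is mostly one of wording. Both points stand. They do not explain section 8.1.2, which presents a value as a severe AE on its size alone, or why the same platelet count is an AE on one scheduled day and a matter of judgement on another.

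The second reply is that a worst-grade or shift table from laboratory data is commonly left to the SAP, which is not among the documents, and that worst-grade listings are already planned. This also stands in part: it cannot be said that such a table is absent from the trial's analyses. But the AE definition is fixed in the protocol, section 7.1.7 names its own safety tables, and all of them rest on AEs. The listings go to an appendix, give no rates, and do not say whether they draw on laboratory data or AE forms.

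A reader might infer that toxicity the dosing rules ignore is simply missing. The documents do not support that, because treatment and investigator judgement remain as routes. A reader might also want to state how many of the 45 patients would be lost. The documents give no basis: the 28% thrombocytopenia and 25% neutropenia in Table 1-3 are all-grade reported events from other combinations.

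**Conclusion.** The point holds in limited form. As written, sections 8.1.1 and 7.1.7 together allow graded laboratory toxicity, mainly haematological, to be under-counted in the co-primary safety tables when it prompts no change in dosing, no treatment and no judgement of significance. The direction is downward and the size cannot be derived from the documents. Apart from the white-cell example, the protocol gives no CTCAE laboratory cut-offs, so no grade is assigned here to the platelet and ANC ranges.

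The conclusion assumes that sites apply section 8.1.1 literally and that the tables are built from AE records, as section 7.1.7 says. It does not extend to the stopping rule, or to related Grade 3 biochemical toxicity, which is largely captured. An SAP that already grades laboratory data directly would remove most of the practical effect, but not the inconsistent wording.

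**What to change.** In section 7.1.7, state that the worst post-baseline CTCAE grade of haematology and biochemistry will be tabulated from the scheduled FBE and biochemistry results, regardless of action taken, alongside the reported-AE tables. Reconcile sections 8.1.1, 8.1.2 and 8.2 so that sites have one rule for reporting a laboratory value as an AE, and so that the white-cell example agrees with it. No dosing rule needs to change for this.

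The cost is one extra programmed table from data already collected and a short wording amendment. The downside is that laboratory toxicity rates may look somewhat higher than those from AE reports alone.
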